## **2. Secondary outcome measures:**

SpO2, HR, MBP, and frequency of vasoactive medication use during anesthesia, and incidence of adverse events in the PACU. Time to the disappearance of the lash reflex after induction.

## **5. Statistical treatment**

### 1. Analyze the crowd

- 1) Full analysis set (FAS): Subject set following the principle of intentional treatment (Intention To Treat, ITT): the data set consisting of all subjects participating in treatment and with baseline efficacy evaluation.
- 2) Compliance with the protocol set (PPS): refers to the completed trial and excluded the treatment population group with serious protocol violations (refers to which the study subjects violated the inclusion criteria or exclusion criteria).
- 3) Safety analysis set (SS): means the set of all subjects enrolled, with a study intervention, and with at least one baseline level safety evaluation.
- 4) Efficacy analysis will be conducted on the basis of the full analysis set and the compliant protocol set. All baseline demographic data analyses will be conducted based on the full

analysis set, and safety evaluations will be conducted on the safety set.

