## 2.2 Sample size estimation:

The primary outcome measure was the quality of postoperative patient recovery (QoR-15 score). According to previous studies, the minimal clinically important difference was 8. The non-inferiority bound for the mean difference between groups was set to -8. Referring to previous studies, the standard deviation (SD) of the QoR-15 scale is 14, and accounting for a 10% shedding rate, 112 achieves 90% of efficacy with a type 1 error of 0.05. We chose to include 112 subjects in this study for the analysis, with 56 subjects in each group.

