## **4. Efficacy Evaluation Criteria**

### **1. Main outcome measures:**

The primary outcome measure was the quality of recovery at 24h after surgery (QoR-15 score), recording the QoR-15 score 1 day before surgery, 1 day after surgery (POD 1) and 2 days after surgery (POD 2). The POD 1 score was the primary study outcome.

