## 2. Statistical analysis method

Data management was performed by EpiData software; SPSS26.0 software was used for statistical analysis. Quantitative variables were tested for normality by using the Shapiro - Wilk test. Comparison of quantitative variables with normal distribution between groups were performed by the t-test, and quantitative data with asymmetric distribution were analyzed by the Mann Whitney U-test. Qualitative variables were compared between groups with the chi-square test or Fisher's exact test as needed. Data for the QoR-15 score are also expressed as the median difference and their 95% confidence interval (CI). Median difference is the median of all pairwise differences between the two sets of observed values, with the 95% CI estimated by Hodges-Lehmann. Data on the frequency of adverse events were reported by the proportion difference and their 95% CI. The 95% CI of proportional differences was calculated using the Wilson program. Among other parameters, such as patient demographic parameters, SpO2, HR, MBP, and vasoactive drug application frequency, median or proportional differences and their 95% CI were calculated as described above. All analyses were assessed using two-sided tests and a P-value less than 0.05 was considered statistically significant.

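### The full analysis set keeps treated patients without a POD 1 score, but the stated tests cannot use them and no missing-data method is given

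*Combined protocol and SAP*

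**What the plan says.** - **FAS** (Statistical treatment, 1. Analyze the crowd, item 1). It is tied to the intention-to-treat principle and defined as "the data set consisting of all subjects participating in treatment and with baseline efficacy evaluation".
- **PPS** (same section, item 2). It "refers to the completed trial and excluded the treatment population group with serious protocol violations", where serious violations means breaches of the eligibility criteria.
- **Use of the sets** (same section, item 4). "Efficacy analysis will be conducted on the basis of the full analysis set and the compliant protocol set".
- **Primary outcome** (Efficacy Evaluation Criteria, 1. Main outcome measures). QoR-15 is recorded the day before surgery, on POD 1 and on POD 2, and "The POD 1 score was the primary study outcome".
- **Method** (Statistical treatment, 2. Statistical analysis method). "Comparison of quantitative variables with normal distribution between groups were performed by the t-test", with Mann-Whitney otherwise. For the effect estimate, "Median difference is the median of all pairwise differences between the two sets of observed values", with a Hodges-Lehmann 95% interval. No covariate or repeated-measures model is mentioned.
- **Expected loss** (2.2 Sample size estimation). The total of 112 was reached "accounting for a 10% shedding rate". Neither the timing nor the reasons for loss are given.

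There is no rule for missing QoR-15 scores, no imputation and no missing-data sensitivity analysis.

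**The concern.** A treated patient with a preoperative score but no POD 1 score is a member of the FAS, yet has no value to enter into any of the named tests. With no rule for such patients, the default is to leave them out, and the set called intention-to-treat is analysed as those who answered on POD 1.

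In a non-inferiority trial the FAS and PPS are analysed side by side so that each can check the other. Here both would rest largely on the same responders. Loss related to outcome and unequal between arms would then shift both results the same way, and agreement between them would not reveal it. A rule chosen after the data are seen would also be open to question.

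The preoperative and POD 2 scores say something about a missing POD 1 score. They are already collected, and the primary analysis does not use them.

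**Working it through.** **Inputs.** From the documents: 112 patients, 56 per arm; margin -8; SD 14; 10% loss; stated power 90% at type 1 error 0.05; two-sided tests at 0.05 with a 95% interval. Assumed, because the documents do not say: true difference 0 for power; for bias, the size and arm of any outcome-related loss.

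**1. The plan's own figure.** 112 x 0.9 = 100.8 analysed, or 50.4 per arm. SE = 14 x sqrt(2/50.4) = 2.789, and 8/2.789 = 2.869.
- One-sided 0.05: Phi(2.869 - 1.645) = 88.9%, close to the stated 90%.
- One-sided 0.025 (the lower limit of a 95% interval): Phi(2.869 - 1.960) = 81.8%.

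If all 112 gave a score, these would be 91.6% and 85.6%. The allowance for loss is already in the sample size, so the issue here is bias more than power.

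**2. How many patients.** 112 - 100.8 = 11.2, so about 11, or 5 to 6 per arm. This is an upper figure at the planned rate. Patients lost before treatment are outside the FAS by definition, and patients lost only at POD 2 still have the primary outcome.

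**3. What separates the two sets.** Without the patients lacking a POD 1 score, the FAS analysis differs from the PPS by eligibility violators and by any patients with a POD 1 score who did not complete the trial. Neither group bears on missing POD 1 scores.

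**4. Size of a possible bias (illustration).** Suppose 10% are missing in each arm, missing remimazolam patients would have scored D points below observed ones, and missing etomidate patients resemble observed ones. The observed difference is then too favourable by 0.1 x D. Take 50 observed per arm, so SE = 14 x sqrt(2/50) = 2.8 with 98 degrees of freedom, and a true difference of exactly -8. The chance of wrongly declaring non-inferiority is P(T > critical value), where T is noncentral t with noncentrality 0.1 x D/2.8.

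| D | Bias | Noncentrality | One-sided 0.025 | One-sided 0.05 |
|---|---|---|---|---|
| 0 | 0 | 0 | 2.5% | 5.0% |
| 5 | 0.5 | 0.179 | 3.7% | 7.1% |
| 10 | 1.0 | 0.357 | 5.4% | 9.8% |
| 14 | 1.4 | 0.500 | 7.2% | 12.5% |
| 20 | 2.0 | 0.714 | 10.5% | 17.5% |

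If the pattern falls on etomidate instead, the sign of the bias reverses and the error rate drops below nominal, at the cost of power.

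**5. What the collected scores can recover.** This was simulated with 4000 runs, true difference -8, and assumed correlations of 0.5 (baseline-POD 1), 0.6 (POD 1-POD 2) and 0.4 (baseline-POD 2). About 8% of remimazolam and 10% of etomidate POD 1 scores were missing, with remimazolam loss more likely at low POD 2 scores.
- POD 2 observed: responders only -7.13; adjusted for baseline and POD 2, -8.00.
- POD 2 also missing: responders only -7.18; adjusted for baseline, -7.44. This removes (7.44 - 7.18)/(8 - 7.18) = 0.26/0.82, about a third of the bias.

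Other assumed dropout slopes put the responders-only estimate between -6.7 and -7.3.

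**The case against.** **The direction of bias is assumed.** This stands. A reader might infer that the gap favours remimazolam, but nothing in the documents shows differential loss. The anesthesiologist, postoperative visitors and patients are blinded (Research methods, 2.1), and the Research Background says etomidate may increase nausea and vomiting and lower satisfaction. Selective loss could fall on that arm and count against non-inferiority.

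**The size is modest.** This stands in part. A 5 to 10 point deficit among missing patients gives 0.5 to 1.0 points of bias against a margin of 8. The error rates apply at a true difference of exactly -8, and with balanced or unrelated loss there is no such inflation.

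**About 11 FAS patients will be dropped.** A reader might take this as fact. The 10% is not split by timing or reason, so 11 is only an upper figure at the planned rate.

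**The FAS and PPS are not identical.** This is correct. The PPS removes eligibility violators, and completing the trial may require a POD 2 score. The comparison keeps some content, but little of it concerns missing POD 1 scores.

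**A standard mixed model would solve it.** Not fully. With baseline as a covariate, a patient with neither postoperative score contributes no outcome and is again excluded. Patients who leave a day-surgery study may well miss both scores; the documents do not say.

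None of these objections supplies the missing rule.

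**Conclusion.** The point holds in a limited form. The plan defines an intention-to-treat set that its stated methods cannot fully analyse, and it gives no method for the gap. The documents do not choose a responder analysis; it is the default left by their silence. Up to about 11 of 112 patients could be affected.

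With 10% missing, SD 14 and outcome-related loss on remimazolam only, the bias would be 0.5 to 2.0 points, with false non-inferiority of 3.7% to 10.5% against 2.5%. The loss pattern is an assumption, and the mirror pattern reverses the effect. The documents therefore support a finding that the primary result is unprotected against informative loss. They do not support a finding that it will be biased toward non-inferiority. The plan should be changed before unblinding; the sample size need not change on this account.

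**What to change.** 1. **Primary FAS analysis.** Estimate the POD 1 difference with a method that keeps every treated patient with a baseline score. Prespecify one of these: multiple imputation by arm using baseline and POD 2 QoR-15, followed by baseline-adjusted ANCOVA; or a longitudinal model with baseline, POD 1 and POD 2 all as outcomes. Compare the lower limit of the 95% interval with -8.
2. **Tipping-point analysis.** Lower the imputed remimazolam POD 1 scores over a range that includes 8 points and extends until the conclusion changes. One 8-point penalty is too weak: at 10% missing it moves the estimate by 0.1 x 8 = 0.8 points. For scale, with an observed difference of 0 and SE 2.8, the lower limit is -1.984 x 2.8 = -5.6, so a penalty of about (8 - 5.6)/0.1 = 24 points would be needed to reach -8, ignoring imputation variance. For patients missing both postoperative scores this analysis is the main safeguard.
3. **Reporting.** Give the number of missing POD 1 scores by arm and reason.
4. **PPS.** Keep the planned responder analysis there.

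The cost is SAP wording and modest extra analysis, with no new data. The sensitivity result may be less favourable than the responder analysis.

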## 2. Statistical analysis method

Data management was performed by EpiData software; SPSS26.0 software was used for statistical analysis. Quantitative variables were tested for normality by using the Shapiro - Wilk test. Comparison of quantitative variables with normal distribution between groups were performed by the t-test, and quantitative data with asymmetric distribution were analyzed by the Mann Whitney U-test. Qualitative variables were compared between groups with the chi-square test or Fisher's exact test as needed. Data for the QoR-15 score are also expressed as the median difference and their 95% confidence interval (CI). Median difference is the median of all pairwise differences between the two sets of observed values, with the 95% CI estimated by Hodges-Lehmann. Data on the frequency of adverse events were reported by the proportion difference and their 95% CI. The 95% CI of proportional differences was calculated using the Wilson program. Among other parameters, such as patient demographic parameters, SpO2, HR, MBP, and vasoactive drug application frequency, median or proportional differences and their 95% CI were calculated as described above. All analyses were assessed using two-sided tests and a P-value less than 0.05 was considered statistically significant.

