### 2. Research methods

2.1 Study design: Randomized, controlled, parallel non-inferiority trial

Randomization: The randomization result was generated by the investigator using R software, sealed to the envelope and handed over by the patient to the anesthesia nurse before surgery, who was responsible for unpacking the randomized envelope.

Blinding: The anesthesia nurse was responsible for unpacking the randomized envelope and preparing drugs to cover the syringes (with the same appearance and volume), and blinded the anesthesiologist, postoperative visitors and patients.

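### No non-inferiority rule in the analysis section: two-sided P<0.05 is the only criterion, and no interval is compared with the -8 bound

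*Combined protocol and SAP*

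**What the plan says.** The design is described as "Randomized, controlled, parallel non-inferiority trial" (2.1 Study design), and 1.2 Study Content says the same. Section 2.2 Sample size estimation gives the bound: "The non-inferiority bound for the mean difference between groups was set to -8". The same section states that "accounting for a 10% shedding rate, 112 achieves 90% of efficacy with a type 1 error of 0.05", without saying whether the 0.05 is one-sided or two-sided. Under 4. Efficacy Evaluation Criteria, "The POD 1 score was the primary study outcome".

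The methods are in 5. Statistical treatment, 2. Statistical analysis method. A Shapiro-Wilk test selects a t-test or, failing normality, a rank test: "quantitative data with asymmetric distribution were analyzed by the Mann Whitney U-test". QoR-15 is additionally reported as a median difference with a 95% interval: "Median difference is the median of all pairwise differences between the two sets of observed values, with the 95% CI estimated by Hodges-Lehmann". The section closes with its only decision criterion: "All analyses were assessed using two-sided tests and a P-value less than 0.05 was considered statistically significant". It mentions neither non-inferiority nor -8. The preceding part of Section 5 assigns efficacy to both the full analysis set (FAS) and the per-protocol set (PPS), but does not say which decides or what happens if they disagree.

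**The concern.** A non-inferiority trial asks whether the new treatment is worse by less than the margin. A two-sided P-value from a t-test or Mann-Whitney test asks whether there is any difference. The plan does not write out a null hypothesis for these tests. Since it mentions no shift by the margin, they are taken here to be ordinary tests of no difference. A non-significant result of that kind does not show that a deficit of 8 points has been excluded.

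Endpoint, bound and an interval are all prespecified. The sentence linking them is missing, and that sentence is the primary hypothesis test. Without it, four choices stay open once data are seen: the confidence level, the scale (mean or Hodges-Lehmann), the test that Shapiro-Wilk selects, and the deciding analysis set.

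**Working it through.** **Inputs.** From 2.2 Sample size estimation: bound -8, SD 14, N = 112 (56 per arm), 10% loss, power 90%, type 1 error 0.05. Assumed: normal data and a true difference of 0 unless stated (the plan gives none). After loss, 112 × 0.9 = 100.8, taken as 50 per arm.

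**1. The plan's own power.** SE = 14√(2/n), which is 2.80 at n = 50 and 2.646 at n = 56. With the normal approximation, power = Φ(8/SE - z).
- One-sided 0.05, n = 50: Φ(2.857 - 1.645) = 88.7%. At n = 56: 91.6%.
- One-sided 0.025, n = 50: Φ(2.857 - 1.960) = 81.5%. At n = 56: 85.6%.

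The stated 90% is therefore approached only at one-sided 0.05, which corresponds to a 90% CI. The analysis section plans a 95% CI.

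**2. Decision boundaries (t-based).** Half-width = t × SE. Non-inferiority passes if the observed difference exceeds -8 + half-width.

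| n per arm | 95% half-width | passes above | 90% half-width | passes above | P≥0.05 down to |
|---|---|---|---|---|---|
| 50 | 5.557 | -2.44 | 4.650 | -3.35 | -5.56 |
| 56 | 5.243 | -2.76 | 4.389 | -3.61 | -5.24 |

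Example with 50 per arm, observed SD 14 and observed difference -3. The lower 95% limit is -3 - 5.557 = -8.56 (fails), the lower 90% limit is -3 - 4.650 = -7.65 (passes), and t = -3/2.80 = -1.07 is non-significant.

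**3. How often the two criteria part.** The quantity is the probability that P≥0.05 while the lower limit is at or below -8. Normal approximation at n = 50, true difference 0, 95% CI: Φ(-2.512/2.80) - Φ(-5.488/2.80) = 0.185 - 0.025 = 0.160. With the SD estimated in each of 2,000,000 simulated trials:

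| True difference | n per arm | 95% CI | 90% CI |
|---|---|---|---|
| 0 | 50 | 16.7% | 9.1% |
| 0 | 56 | 12.5% | 6.2% |
| -4 | 50 | 41.4% | 29.6% |
| -4 | 56 | 35.6% | 23.5% |

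These trials fail non-inferiority under a correct rule and are also non-significant. They become wrong conclusions only if non-significance is taken as success.

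**4. If P≥0.05 were read as no worse.** The documents do not say this; the figure is conditional. At a true difference of -8, P≥0.05 occurs in 19.2% of trials (n = 50) or 15.0% (n = 56). A proper rule accepts 2.5% (95% CI) or 5% (90% CI). The ratio runs from 0.150/0.05 = 3.0 to 0.192/0.025 = 7.7.

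**5. Scale.** The mean difference and the Hodges-Lehmann shift coincide under a pure location shift. With normal data and a true difference of 0, their 95% intervals disagree about -8 in 5.3% (n = 50) or 4.4% (n = 56) of 40,000 simulated trials. Outside a location shift the gap can be larger. As an illustration only, suppose 20% of remimazolam patients score 40 points lower and the rest are unchanged. The mean difference is 0.2 × (-40) = -8.0, while the Hodges-Lehmann shift is -5.76.

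**6. Power under an explicit rule, true difference 0** (noncentral t for the mean, simulation for Hodges-Lehmann; 50 per arm, with 56 per arm in brackets):

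| Scale | 95% CI | 90% CI |
|---|---|---|
| Mean | 80.8% (85.0%) | 88.3% (91.3%) |
| Hodges-Lehmann | 78.3% (83.3%) | 86.6% (90.3%) |

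**The case against.** The best reply is that the rule can be inferred. The Research Background says recovery should be no worse than with etomidate. Higher QoR-15 is better, so a negative bound implies remimazolam minus etomidate. POD 1 is fixed and a 95% CI is planned. On this view the closing P-value sentence is general wording for every variable in the trial, and only one line is missing. It is true that non-inferiority could still be judged from what is prespecified. But inference settles neither the level nor the scale: the stated power points to a 90% CI on the mean, and the planned interval is a 95% CI on the Hodges-Lehmann shift. As written, the P-value sentence also covers all analyses.

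Some limits on the figures stand. The threefold to eightfold false-positive ratio depends on a reading the documents do not contain, so the case does not rest on it. Disagreement between scales is small under normality. The mixture example shows possibility, not likelihood: its remimazolam arm has SD √(14² + 0.2 × 0.8 × 40²) = √452 = 21.3, not 14. Sidedness of alpha, the FAS/PPS rule and normality pre-testing could each be raised separately. They appear here because a complete decision rule has to settle them.

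**Conclusion.** The concern holds. The stated criterion is the wrong test for the stated objective, and no other section supplies the right one. Because this is the primary hypothesis test, it must be corrected. With SD 14, normal data and 50 evaluable patients per arm, observed mean differences from about -5.6 to -2.4 are non-significant yet fail a 95% CI rule. Those between -3.35 and -2.44 pass or fail according to the unstated confidence level. The advertised 90% power is not delivered by the planned 95% interval: at a true difference of 0 it gives 81% on the mean scale or 78% on the Hodges-Lehmann scale after 10% loss, and 85% or 83% with no loss.

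**What to change.** Add a decision rule to 5. Statistical treatment, 2. Statistical analysis method: *Non-inferiority is concluded if the lower limit of the two-sided 95% CI for the POD 1 QoR-15 difference, remimazolam minus etomidate, is above -8.* Then:

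- Fix one scale in advance. Either use the mean difference, matching 2.2, with Hodges-Lehmann as a sensitivity analysis; or keep the Hodges-Lehmann shift and restate the -8 bound on that scale in 2.2.
- Apply the rule whatever the Shapiro-Wilk result.
- State how FAS and PPS results combine.
- Limit the P<0.05 sentence to secondary comparisons.
- State the sidedness of alpha in 2.2. Either keep the 95% CI (one-sided 0.025) and restate the power, or declare one-sided 0.05 and replace the 95% CI in the rule with a 90% CI.

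**Cost.** These are wording changes and a less favourable stated power; at N = 112 they need no extra patients, data or software. Requiring both FAS and PPS to pass can only lower power further. Keeping 90% power would need more patients. On the mean scale, by normal approximation, n per arm = 2 × 14² × (z_α + 1.282)²/8². This gives 65 per arm for a 95% CI (73 after dividing by 0.9; 146 in total) or 53 per arm for a 90% CI (59 after dividing by 0.9; 118 in total).

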## **3. Observation Items And Monitoring Time Point**

### **1. 1. Baseline metrics**

The following data were collected during the patient screening period

Demographic data: age (yr), gender, education level, ASA grade, body mass index, diagnosis and preoperative comorbidities, and history of smoking and alcohol abuse.

Preoperative clinical data: pulse oxygen saturation (SpO2), Non-invasive blood pressure (NIBP), heart rate and other vital signs, and electrocardiogram.

The following data will be collected during the surgical treatment period:

SpO2, HR, systolic blood pressure, diastolic blood pressure, MBP, test time points including 5 minutes before induction of anesthesia, 1 minute after induction, 1 minute after laryngeal mask placement, and start of surgery. Where, data recorded 5 min before induction of anesthesia served as baseline.

The following data were collected during the PACU recovery period:

SpO2, HR, systolic BP, diastolic BP, and MBP

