### **2. 3. Secondary outcome measures:**

SpO2, HR, MBP, and frequency of vasoactive medication use during anesthesia, and incidence of adverse events in the PACU. Time to the disappearance of the lash reflex after induction.

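### All secondary analyses are judged at an unadjusted P<0.05 with no ordering or exploratory label; if about 12 to 15 are tested, a false-positive secondary result has roughly a one-in-three to one-in-two chance

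*Combined protocol and SAP*

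**What the plan says.** The last sentence of the Statistical analysis method section (part 5, item 2) reads: "All analyses were assessed using two-sided tests and a P-value less than 0.05 was considered statistically significant". It makes no exception for secondary outcomes, safety data or baseline variables.

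The Secondary outcome measures section (part 3) names SpO2 together with "HR, MBP, and frequency of vasoactive medication use during anesthesia, and incidence of adverse events in the PACU", and then "Time to the disappearance of the lash reflex after induction". That is six items: three vital signs recorded repeatedly and three single outcomes.

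The Baseline metrics section (part 3) gives the intraoperative schedule as "test time points including 5 minutes before induction of anesthesia, 1 minute after induction, 1 minute after laryngeal mask placement, and start of surgery", and states that "data recorded 5 min before induction of anesthesia served as baseline". Three readings therefore follow induction. Vital signs are also recorded later, under the line "The following data were collected during the PACU recovery period". The number of PACU readings is not given, and PACU vital signs are not among the named secondary outcomes.

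On method, "Comparison of quantitative variables with normal distribution between groups were performed by the t-test", with Mann-Whitney, chi-square or Fisher's exact test for other data. The section names no repeated-measures model and no summary of serial readings. It does plan differences with 95% CIs for adverse events, the vital signs, vasoactive drug use and demographic variables.

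There is one primary outcome, the QoR-15 score on POD 1 (part 4, Main outcome measures).

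**The concern.** The secondary outcomes carry part of the trial's case. The Research Background says remimazolam would be a new option if it gives haemodynamic stability at induction, avoids etomidate's side effects, and leaves recovery no worse. Only the last condition is the primary outcome. The first rests on the secondary list and the second mainly so.

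Under the plan's rule, one P-value below 0.05 at one reading, favouring either drug, counts as significant. It would count even if non-inferiority on QoR-15 were not shown. Nothing tells a reader which secondary result was meant to carry weight, or how many comparisons were made to find it.

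The rule also reaches the demographic variables. Under randomization any baseline difference arises by chance, so a P-value there tests a hypothesis already known to be true.

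**Working it through.** The plan gives no overall error rate for its secondary outcomes, so there is no stated figure to reproduce. The check derives one.

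**Inputs from the documents**
- Threshold: two-sided 0.05 for every analysis (Statistical analysis method).
- Repeated variables: SpO2, HR, MBP (Secondary outcome measures).
- Single outcomes: vasoactive drug use, PACU adverse events, lash-reflex time (same section).
- Post-induction readings: 3, since the first of the four listed is baseline (Baseline metrics).

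**Assumptions not in the documents**
- One two-group test per reading.
- Adverse events tested once, as an overall incidence.
- The correlation between test statistics. No value is given, so a range is shown.

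**Counting tests**
- Named outcomes during anesthesia: 3 signs × 3 readings + 3 single outcomes = 12.
- Adding one PACU reading of each sign: 3 × 4 + 3 = 15.
- Each of the six named items tested once: 6.

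**Independent tests.** P(at least one P<0.05) = 1 − 0.95^k.
- k = 6: 1 − 0.95^6 = 26.5%
- k = 12: 1 − 0.95^12 = 1 − 0.540 = 46.0%
- k = 15: 1 − 0.95^15 = 1 − 0.463 = 53.7%

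**Correlation ρ between readings of the same vital sign, all else independent.** Let G be the probability that none of the m readings of one sign reaches |z| > 1.96, from equicorrelated normal statistics:

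G = ∫ φ(x) [Φ((1.96 − √ρ·x)/√(1−ρ)) − Φ((−1.96 − √ρ·x)/√(1−ρ))]^m dx

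P(at least one) = 1 − G³ × 0.95³.

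| ρ | 12 tests (m = 3) | 15 tests (m = 4) |
|---|---|---|
| 0 | 46.0% | 53.7% |
| 0.5 | 42.6% | 48.4% |
| 0.7 | 39.4% | 43.6% |
| 0.9 | 34.0% | 36.2% |

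For example, at ρ = 0.9 and m = 3, G = 0.9164, so 1 − 0.9164³ × 0.95³ = 1 − 0.770 × 0.857 = 34.0%.

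**One correlation shared by all outcomes.** The same integral with m equal to the total number of tests:

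| ρ | 12 tests | 15 tests |
|---|---|---|
| 0.5 | 32% | 36% |
| 0.7 | 23% | 26% |
| 0.8 | 19% | 20% |

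**Baseline.** The plan does not fix the number of comparisons. If about 10 were tested independently, 1 − 0.95^10 = 40% would be the chance of at least one spurious imbalance.

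**The case against.** The strongest defence has four parts.

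1. **Testing at each reading is not written.** The schedule says when values are recorded; the analysis section says which tests are used. A reader might infer that every variable is tested at every time point, but the documents do not state this. It remains the natural reading, because two-group tests can handle serial values only one reading at a time or through a summary, and no summary is defined. The percentages are therefore conditional on it.

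2. **The count is not a floor of 15.** A reader might infer at least 15 tests by including PACU vital signs, or 23 (69% if independent) by adding systolic and diastolic pressure. All of these are collected, but none is a named secondary outcome; the named outcomes give 12. Testing adverse events by type would raise the count, but the plan does not say that this is done.

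3. **The correlations are assumed.** Vasoactive drug use and MBP are related, so treating different outcomes as independent overstates the risk to some degree. A high correlation shared by outcomes as unlike as SpO2, lash-reflex time and adverse events is the less plausible extreme, but the documents cannot rule it out. Fisher's exact test on rare events is conservative and would lower the figures further.

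4. **The outcomes are labelled secondary, and CIs are already planned.** Both are true. Nothing calls these outcomes confirmatory, and half the remedy is in place. What stands is that the closing sentence still attaches a significance verdict to each of them.

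**Conclusion.** The point holds as a fault in how secondary findings will be declared. The plan labels any P below 0.05 significant, in every analysis, without adjustment, ordering or an exploratory label.

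If each post-induction reading is tested, the chance of at least one false-positive secondary result when the drugs do not differ is about 34-46% for 12 tests and 36-54% for 15. These ranges assume within-variable correlations from 0.9 down to 0 and independence between outcomes. With a correlation of 0.7-0.8 shared by all outcomes the chance is about 19-26%. With six independent tests it is 26%. Every one of these scenarios is well above 5%.

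Two stronger readings are not supported. A reader might take the 36-54% as the chance of a false haemodynamic or safety finding, but it includes lash-reflex time, which is neither. Without that outcome the independent figures are 1 − 0.95^11 = 43% and 1 − 0.95^14 = 51%. A reader might also infer that the trial's main conclusion is compromised. It is not: there is one primary outcome at one time point, and testing secondary outcomes does not change its type I error.

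**What to change.** Replace the last sentence of the Statistical analysis method section with wording to this effect: statistical significance will be claimed only for the primary outcome, QoR-15 on POD 1; secondary outcomes will be reported as the planned between-group differences with 95% CIs, labelled exploratory, and not described as significant; baseline characteristics will be summarised by group without P-values.

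If the sponsor wants one confirmatory haemodynamic claim, it may name in advance a single key secondary outcome of its own choice, with variable and time point, tested at two-sided 0.05 only after non-inferiority has been shown. This step is optional; the exploratory label alone resolves the point.

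The section should also say whether the vital signs are compared at each reading or through a defined summary, so that the number of comparisons is known.

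Cost: one paragraph of text, with no new data or patients. The downside is that fewer secondary results can be called significant.
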